### 7.1.3.2. Sensitivity Analysis

Sensitivity analysis will be performed on the ITT population with multiple imputations. The missing data in A1C measurements will be handled by the multiple imputation approach using imputation regression method, where the independent variables in the regression model are age, gender, baseline A1C and BMI. In each imputed dataset, the missing A1C data will be imputed by  $\hat{y} + z\hat{\sigma}$ , where  $\hat{y}$  is the predicted value from regression,  $Z$  is a standard normal random variable,  $\hat{\sigma}$  is the estimated standard deviation of the random residual from the regression model. The imputation

will be performed five times using the MI procedure and the analysis results will be combined to form one inference using the MIANALYZE procedure in SAS 9.3.

### 7.1.3.3. Descriptive Statistics

The primary endpoint will also be summarized (descriptive statistics) and stratified by:

- Investigational Site
- Age
  - Adults age 22 and older
  - Adolescents age 16-21
- Ethnicity
  - Hispanic/Latino
  - Non-Hispanic/Non-Latino
  - Subject refused
- Race
  - American Indian/Alaska Native
  - Black/African-American
  - White - anticipated maximum less than 80%
  - Native Hawaiian/Other Pacific Islander
  - Asian
  - Other
  - Subject refused
- Baseline BMI according to WHO criteria [World Health Organization, 2011]
  - Underweight subjects (BMI less than 18.5 kg/m^2)
  - Normal weight subjects (BMI 18.5 to 24.99 kg/m^2):
  - Overweight subjects (BMI 25.00 to 29.99 kg/m^2)
  - Obese subjects (BMI 30.00 to 39.99 kg/m^2)
  - Morbidly obese subjects (BMI greater than or equal to 40 kg/m^2)
- Gender
  - Male
  - Female
- Diabetes Classification
  - Diabetes type 1
  - Diabetes type 2
  - Other diagnosis of Diabetes
- Duration of Diabetes
  - Duration of diabetes less than 20 years
  - Duration of diabetes greater than or equal to 20 years
- Hypoglycemic Unawareness Questionnaire
  - Patients with intact hypoglycemic awareness (95% confidence interval will be provided)

- Patients who have impaired hypoglycemic awareness (95% confidence interval will be provided)
- Transition Groups
  - Subjects who have been exposed to the 530G pump therapy with the TS feature ON for 7 days or less prior to screening
  - Subjects who have been exposed to the 530G pump therapy with the TS feature ON for 8 to 365 days prior to screening

#### **7.1.4. Safety Analysis for Multi-Center Trial**

All adverse events reported by the site per protocol for enrolled subjects will be summarized. The summary will include all adverse events and adverse events by: Insulin Pump Infusion set; Insulin administration and pump use; Sensor Use; Severe Hypoglycemia; Severe Hyperglycemia; Diabetic Ketoacidosis; Adverse Device Event; Serious Adverse Event and Unanticipated Adverse Device Effect. Adverse Events by Investigator will also be provided. No formal statistical analysis will be carried out.

In addition, data will be collected for a descriptive summary of device disposition; adverse events; device performance and user acceptance. Safety analysis will include a summary of the following:

All Adverse events to be collected include the following:

- Adverse Events related to the study device
- Adverse Events related to study procedures
- Serious Adverse Events (SAE)
- Unanticipated Adverse Device Effects (UADE)
- Incidence of Severe Hypoglycemia
- Incidence of Severe Hyperglycemia
- Incidence of Diabetic Ketoacidosis (DKA)

#### **Adverse Events will be stratified by**

- Age
  - Adults age 22 and older
  - Adolescents age 16-21
- Ethnicity
  - Hispanic/Latino
  - Non-Hispanic/Non-Latino
  - Subject refused
- Race
  - American Indian/Alaska Native
  - Black/African-American
  - White - anticipated maximum less than 80%
  - Native Hawaiian/Other Pacific Islander)
  - Asian
  - Other

- Subject Refused
- Baseline BMI according to WHO criteria [World Health Organization, 2011]
  - Underweight subjects (BMI less than 18.5 kg/m)
  - Normal weight subjects (BMI 18.5 to 24.99 kg/m^2)
  - Overweight subjects (BMI 25.00 to 29.99 kg/m)
  - Obese subjects (BMI 30.00 to 39.99 kg/m)
  - Morbidly obese subjects (BMI greater than or equal to 40 kg/m^2)
- Gender
  - Male
  - Female
- Diabetes Classification
  - Diabetes type 1
  - Diabetes type 2
  - Other diagnosis of Diabetes
- Duration of Diabetes
  - Duration of diabetes less than 20 years
  - Duration of diabetes greater than or equal to 20 years
- Hypoglycemic Unawareness Questionnaire
  - Patients with intact hypoglycemic awareness (95% confidence interval will be provided)
  - Patients who have impaired hypoglycemic awareness (95% confidence interval will be provided)
- Frequency and average duration of hypoglycemic event (based on two weeks prior to the adverse event)
- The actual one-sided 95% upper confidence limit of severe adverse event incidence rate (DKA and severe hypoglycemia) will be calculated. Individual one-sided 95% confidence limit for DKA only and severe hypoglycemia only will also be provided. Please note: the planned analysis may not be adequate since we did not meet the defined minimum sample size requirement.

### **7.1.5. Secondary Endpoint for Multi-Center Trial**

The mean change in A1C from baseline to 3-month, 6-month, 9-month and 12-month will be summarized individually for each of the three baseline A1C cohorts:

- A1C less than 7.0%;
- A1C between 7.0% to 9.0%;
- A1C greater than 9.0%

### **7.1.6. Descriptive Endpoints for Multi-Center Trial**

Descriptive Summary Statistics will be provided.

**A1C Change:**

- The percentages of subjects with increased A1C and decreased A1C from baseline will be presented for each baseline A1C subgroup (less than 7%, 7% – 9% and greater than 9%) and overall.
- The distribution of subjects' changes in A1C will also be summarized by histogram for each baseline A1C subgroup and overall.

**TS Metrics – Hypoglycemia Endpoints:**

Hypoglycemic Event Incidence, where an event is identified by the following criteria within 4 hours that TS is activated:

- CGM value less than or equal to 70 mg/dL continuously for greater than 20 minutes
- The rate of change (defined by the change between two consecutive sensor glucose measurements) will be examined during the 10 minute time interval before reaching a sensor glucose value of less than or equal to 70 mg/dL. If any rate of change in sensor glucose is  $>5$  mg/dl/minute, the event will not be counted
- When the time between two successive events is less than 30 minutes, they will be combined as one event

The above information will be repeated for hypoglycemia threshold at 40, 50, 60, 65 and 70 mg/dL with and without TS activation and will be summarized by Day (8:00am – 10:00pm) /Night (10:00pm – 8:00am) and TS Threshold Settings.

The hypoglycemic event incidence, duration and the percentage of time spent (below TS threshold setting) within 4-6 hours of suspend will also be summarized. The hypoglycemic event is identified as:

- CGM value below the TS threshold continuously for at least 20 minutes
- No evidence of patient intervention which includes meter BG, meal marker and insulin delivery change during the first 20 minutes when CGM value is below the TS threshold.
- When the time between two successive events is less than 30 minutes, they will be combined as one event

Data will be summarized for each baseline A1C subgroup (less than 7%, 7%-9% and greater than 9%) and overall.

**TS Metrics – Hyperglycemia Endpoints:**

Hyperglycemic Event Incidence, where an event is identified by the following criteria within 4 hours that TS is activated:

- CGM value greater than or equal to 180 mg/dL continuously for greater than 20 minutes.
- The rate of change (defined by the change between two consecutive sensor glucose measurements) will be examined during the 10 minute time interval before reaching a sensor glucose value of greater than or equal to 180 mg/dL. If any rate of change in sensor glucose is  $>5$  mg/dl/minute, the event will not be counted
- When the time between two successive events is less than 30 minutes, they will be combined as one event

The above information will be repeated for hyperglycemia threshold at 180, 250, 300, 350 and 400 mg/dL with and without TS activation and will be summarized by Day (8:00am – 10:00pm) /Night (10:00pm – 8:00am) and TS Threshold Settings. The hypoglycemic event incidence, duration and the percentage of

time spent (below TS threshold setting) within 4-6 hours of suspend will also be summarized. The data will be summarized for each baseline A1C subgroup (less than 7%, 7%-9% and greater than 9%) and overall.

**Device Utilization:**

- We will provide descriptive summary statistics of suspend event including frequency, mean change of SG values before and after the suspense.
- TS Setting ON/OFF
- TS Threshold Setting
- Number of occurrences and time of Insulin Delivery Suspension by TS suspension/manual suspension (unrelated to the threshold suspend feature)
  - Manual suspension
  - Temporary basal set to zero
  - Threshold Suspend without user acknowledgement
  - Threshold Suspend acknowledged by user and cancelled
  - Threshold Suspend acknowledged by user and confirmed
  - Threshold Suspend first acknowledged by subject and confirmed, the followed by a second Threshold suspend not acknowledged by the subject after the hypoglycemia repeat time has elapsed.
- Subject response to insulin suspension
  - Confirmatory SMBG compliance during TS (within 2 hours of alarm) by length of time after the alarm (every 30 min up to 4 hours from TS activation)
  - Length of time to acknowledge TS alert by day and night
  - Comparison of time of alarm, time to SMBG and effects on glycemia
- Therapeutic change in basal insulin (within 2 hours of alarm)
  - Frequency of basal increase/decrease/no change;
  - Summary statistics of amount of basal increase/decrease
- Frequency of Sensor Dislodgement / Suspected Occlusion
- Early infusion set change (before 3 days)
- Frequency of infusion set changes
- Frequency of Infusion Set occlusion alarms
- Total suspend time including manual suspends, times when the subject sets a temporary basal rate of zero, and threshold suspends separately and together during the nighttime, daytime, and 24 hour periods.
- Frequency of repeated threshold suspends with 1)  $\leq 15$  minutes and 2)  $\leq 60$  minutes of basal insulin delivery between suspends.
- Repeated threshold suspends with total suspend durations of  $\leq 1$  hour,  $1-\leq 2$  hours,  $2-\leq 4$  hours,  $4-\leq 6$  hours, etc. Please calculate “total suspend durations” as the sum of the durations of repeated suspensions with 1)  $\leq 15$  and 2)  $\leq 60$  minutes between suspends (intervening basal delivery time should not be included).

**CGM Metric:**

- CGM Adherence – average sensor wear per week
- Comparison between CGM data and Glucose Meter data

**Device Performance**

- All complaints that are reported via the 24-hour HelpLine will be summarized and reported.

**Effectiveness of educational materials**

- Subject Questionnaire at Screening
- Subject Questionnaire After Training Session and Device Placement

**Human Factors:**

- Frequency of subject acknowledging the alarm and continuing the suspend, when the suspend occurred automatically (without subject interaction)
- Frequency of subject not continuing the Threshold Suspend and instead manually suspending insulin delivery or setting a temporary basal rate of zero

**Questionnaires:**

The following will be performed on each questionnaire:

1) EQ-5D and EQ-5D-Y

- Summary of changes in score from baseline to end of study will be performed.

2) Low Blood Sugar Survey (Adult, Parent and Child)

- Summary of changes in score from baseline to end of study will be performed.

3) Subject Questionnaire at Screening and Subject Questionnaire after Training Session and Device Placement (training evaluation questionnaire)

- Summary of answers that will be provided no more than 2 hours before and 2 hours after placement of 530 G pump in order to assess effectiveness of training materials.

4) Hypoglycemia Unawareness Questionnaire

- Summary of changes in score from baseline to end of study will be performed.

**7.2. Commercial Data Evaluation: Carelink Database Analysis**

Analysis from the Carelink database with patients on the MiniMed 530G system intends to provide a large heterogeneous source of data taken from the actual commercial use with MiniMed 530G. The focus of this analysis is to provide a robust data set on the safety of this system. To this end, our analysis will not only provide a summary of glucose control and correlation with the use of the Threshold Suspend (TS) feature but will provide a focused analysis on key aspects of the MiniMed 530G system as it relates to the safety of the system.

Datasets will come from MiniMed 530G patients and insulin pumps sold and uploaded within date windows.

## 7.2.1. Primary Safety Endpoint

The difference in self-reported first A1C and subsequent A1C collected from StartRight program. The mean difference in A1C will be estimated and compared by a non-inferiority test with a significance level of 0.025 (one-sided).

The overall difference in A1C will be estimated and compared by a non-inferiority test with an A1C margin of 0.4% and a significance level of 0.025 (one-sided). The null hypothesis will be rejected if the one-sided 97.5% upper confidence limit of the mean difference in A1C is less than 0.4%

The hypothesis is mathematically expressed as:

Ho:  $\mu \geq 0.4\%$

Ha:  $\mu < 0.4\%$

Where 0.4% is the pre-specified non-inferiority margin,  $\mu$  is the mean of difference in A1C (%).

Primary safety endpoint will be presented and tested using pair t-test on those subjects with both first and subsequent A1c.

Descriptive subgroup analysis of A1c data will be performed on demographic cohorts (age, gender, duration of diabetes and years on insulin), and first A1c (less than 7.0%, 7.0-9.0%, greater than 9.0%)

This analysis addresses the primary and secondary safety endpoint per conditions of approval in FDA 530G approval letter

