#### 7.1.2. Study Populations

##### 7.1.2.1. Intention to Treat (ITT) Population

The Intention to Treat (ITT) population will include all enrolled subjects.

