### 7.2.5. **Data Completeness**

Missing demographic measures (Age, gender, Age at Diabetes Onset, Years on Insulin and baseline A1C at entry) for Carelink dataset will be summarized and presented.

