7.4 Handling of Missing Data

For ITT population, the missing data in A1C measurements will be handled by the multiple imputation approach using imputation regression method, where the independent variables in the regression model are age, gender, baseline HbA1C and BMI. The imputation will be performed five times using the MI procedure and the analysis results will be combined to form one inference using the MIANALYZE procedure in SAS 9.4. The primary analysis population for the change in A1C endpoint will be the ITT population with multiple imputations.

All available device data will be used for the analysis. No imputation will be applied for the device data.

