7.8.1 Primary Safety Endpoint

The difference in self-reported first A1C and subsequent A1C collected from StartRight program. The mean difference in A1C will be estimated and compared by a non-inferiority test with a significance level of 0.025 (one-sided).

The overall difference in A1C will be estimated and compared by a non-inferiority test with an A1C margin of 0.4% and a significance level of 0.025 (one-sided). The null hypothesis will be rejected if the one-sided 97.5% upper confidence limit of the mean difference in A1C is less than 0.4%

The hypothesis is mathematically expressed as:

Ho: $\mu \geq 0.4\%$

Ha: $\mu < 0.4\%$

Where 0.4% is the pre-specified non-inferiority margin, μ is the mean of difference in A1C (%).

Primary safety endpoint will be presented and tested using pair t-test on those subjects with both first and subsequent A1c.

Descriptive subgroup analysis of A1c data will be performed on demographic cohorts (age, gender, duration of diabetes and years on insulin), and first A1c (less than 7.0%, 7.0-9.0%, greater than 9.0%)

This analysis addresses the primary and secondary safety endpoint per conditions of approval in FDA 530G approval letter

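### The commercial A1C safety test leaves out every user without a subsequent A1C, and the plan neither requires these users to be counted nor checks what leaving them out could do to the result

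*Protocol*

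**What the plan says.** The endpoint in Protocol 7.2.1 is "The difference in self-reported first A1C and subsequent A1C collected from StartRight program". It is a one-sided non-inferiority test at 0.025 with a margin of 0.4% A1C. The analysis set is fixed in one sentence: "Primary safety endpoint will be presented and tested using pair t-test on those subjects with both first and subsequent A1c". SAP 7.8.1 agrees: "tested using pair t-test on those subjects with both first and subsequent A1c".

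Protocol 7.2 describes the source population: "Datasets will come from MiniMed 530G patients and insulin pumps sold and uploaded within date windows". Neither document says when StartRight collects the subsequent value, by what procedure, or whether people who have stopped the pump are still asked.

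On completeness, Protocol 7.2.5 states: "Missing demographic measures (Age, gender, Age at Diabetes Onset, Years on Insulin and baseline A1C at entry) for Carelink dataset will be summarized and presented". SAP 7.8.5 gives the same list. The subsequent A1C is not on it.

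The only method for missing A1C values belongs to the multi-center trial. SAP 7.4 reads: "For ITT population, the missing data in A1C measurements will be handled by the multiple imputation approach using imputation regression method". Protocol 7.1.2.1 defines that population: "The Intention to Treat (ITT) population will include all enrolled subjects". Protocol 7.1.3.2 and SAP 7.2.1.1 apply the same imputation to the trial's A1C endpoint. Nothing comparable is planned for the commercial A1C endpoint.

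**The concern.** Having a second A1C decides who enters this primary safety test, yet it is the one A1C item whose absence the plan does not ask to be summarized. Missing values are unlikely to be random in commercial data. Whether a user supplies a later A1C may depend on how the user is doing, on staying with the system, or on insurance and cost. Protocol 7.2.3.1 and 7.2.3.2 already name insurance and cost as limits on sensor wear and fingerstick testing.

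The commercial data were added because the trial enrolled 426 subjects against an anticipated 1000, and Protocol 7.2.1 ties this analysis to the safety endpoints in the device's approval conditions. If users without a second value did worse, the paired mean is optimistic as an estimate for all users with a first A1C. The test could then support a claim of no glycemic deterioration that the wider group does not bear out, and no planned output would test for that.

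**Working it through.** **Inputs.** Margin 0.4%, one-sided alpha 0.025, SD of change 1%, assumed mean 0 and 200 subjects (Protocol 7.2.6.1, SAP 7.8.6.1). The share p of users with a first A1C who also have a second is not given, so the values of p below are assumptions.

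**1. The plan's own figure.** For a paired difference, power is approximately Φ(0.4·√n / SD − 1.96). With n = 200 and SD = 1 this is Φ(5.657 − 1.960) = Φ(3.697) = 99.99%. The noncentral t gives 99.99% as well. The stated power of over 95% is right, and 84 pairs would already reach 95%. Sample size is not the problem.

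**2. What passes.** With 200 pairs the upper limit lies 1.972 / √200 = 0.139 above the observed mean (SD 1%). The test passes for any observed mean below 0.4 − 0.139 = 0.261.

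**3. Tipping value for the mean.** Let m be the mean change in the pairs and d the mean change in users without a second value. The all-user mean is p·m + (1 − p)·d. Setting it to 0.4 gives d = (0.4 − p·m) / (1 − p).

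**4. Tipping value for the upper limit.** The test uses the upper limit, so this is the quantity to report. Treating p and d as fixed, with 200 pairs and an observed mean of 0, the all-user upper limit is p × 0.139 + (1 − p)·d. It reaches 0.4 at d = (0.4 − 0.139·p) / (1 − p). For p = 50%, d = (0.4 − 0.0695) / 0.5 = 0.66.

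| p | Mean tips, m = 0 | Mean tips, m = 0.1 | Upper limit tips, m = 0 |
|---|---|---|---|
| 20% | 0.50 | 0.475 | 0.47 |
| 30% | 0.57 | 0.53 | 0.51 |
| 50% | 0.80 | 0.70 | 0.66 |
| 80% | 2.0 | 1.6 | 1.44 |

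**5. Chance of a false pass.** Suppose the all-user mean is exactly 0.4 and users without a second value are 0.5 points worse than the pairs. The pairs' mean is then 0.4 − 0.5·(1 − p). The chance that 200 pairs pass (noncentral t, SD 1%), against a nominal 2.5%, is:

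- p = 90%, pairs' mean 0.35: 10.5%
- p = 80%, pairs' mean 0.30: 29%
- p = 70%, pairs' mean 0.25: 56%
- p = 50%, pairs' mean 0.15: 94%

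More pairs do not help. At p = 80% the chance rises from 29% with 200 pairs to 88.5% with 1000, because the interval tightens around the wrong mean.

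**The case against.** A reader might infer that users who stopped the 530G have no second A1C and so vanish from the test. The documents do not say so. Someone who stopped could still have reported a value, and someone who continued could lack one. Restricting the data to pumps uploaded in a date window makes loss of stoppers plausible but does not establish it. That part of the objection stands, and the point here is limited to users without a subsequent A1C, whatever the reason.

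A reader might also infer that the report would hide the response share altogether. That goes too far. The missing-baseline summary and the number of pairs in the test might let a reader work it out. But the plan does not require the share, and it does not say that the StartRight and CareLink denominators agree.

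The target population is arguable too. The objective concerns home use of TS, and A1C after leaving the system partly reflects other therapy. A mean over all users with a first A1C is a legitimate target, but sub-study 2 does not name it. This is a reason to state the population, not to leave it open.

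Finally, this test does not stand alone. The plan has sensor-estimated A1C with TS ON versus OFF, a co-primary test on time above 180 mg/dL, hospitalization rates, and the trial's own central-laboratory A1C with imputation. These reduce the weight on this test. They do not replace a missing-data check on it, and the sensor analyses carry selection of their own.

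**Conclusion.** The point holds as a gap in the analysis plan. The commercial A1C test is limited to complete pairs, the completeness list omits the value that defines those pairs, and no sensitivity analysis covers missing second values.

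How much this matters depends on p, which is unknown. At p = 20% to 30%, an average worsening of about half a point in users without a second value takes the all-user mean to 0.4%. At p = 80% it would take 2.0 points, and a paired mean of zero would be hard to overturn. These figures assume zero mean change in the pairs. The false-pass rates also assume an SD of 1% and a 0.5-point gap. The documents do not show that excluded users did worse, and the bias could run the other way.

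The risk concerns the mean over all users with a first A1C. It would be wrong to read it as saying that every user who started could have deteriorated beyond the margin while the test passes. The stated power is correct and is not in question.

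**What to change.** - **Protocol 7.2.5 and SAP 7.8.5:** add subsequent A1C to the completeness list. Report the number of users with a first A1C and the number with both. Compare first A1C, age, gender and duration of diabetes between users with and without a second value. Add TS utilization and date of last upload where StartRight and CareLink records can be linked, since the documents do not describe that linkage. Last upload is only a rough indicator of stopping, because a user can stop uploading and keep using the pump.
- **Protocol 7.2.1 and SAP 7.8.1:** keep the paired t-test and the margin. Add a tipping-point sensitivity analysis giving the mean change in users without a second A1C at which the 97.5% upper limit for all users with a first A1C reaches 0.4%.
- **Conclusion:** state in advance that, if the tipping value is plausible given the response share, the conclusion is limited to users who reported a subsequent A1C.

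The cost is a little more analysis and possibly a narrower claim. The sample size does not change.
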